## PROTOCOL AMENDMENT SUMMARY OF CHANGES

### DOCUMENT HISTORY

| Document                                | Country/countries impacted by amendment | Date, version                           |
|---|---|---|
| Amended Clinical Trial Protocol 03      | All                                     | 28-Jan-2020, version 1 (electronic 3.0) |
| Amended Clinical Trial Protocol 02      | All                                     | 24-Jul-2019, version 1 (electronic 2.0) |
| Amended Clinical Trial Protocol 01      | All                                     | 27-Feb-2018, version 1 (electronic 1.0) |
| Amended Clinical Trial Protocol 02 (US) | US only                                 | 27-Feb-2018, version 1 (electronic 3.0) |
| Protocol Amendment 02                   | All                                     | 27-Feb-2018, version 1 (electronic 1.0) |
| Amended Clinical Trial Protocol 01 (US) | US only                                 | 23-Mar-2016, version 1 (electronic 2.0) |
| Protocol Amendment 01 (US)              | US only                                 | 23-Mar-2016, version 1 (electronic 2.0) |
| Clinical Trial Protocol                 | All                                     | 11-Apr-2014, version 1 (electronic 1.0) |

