### OVERALL RATIONALE FOR THE AMENDMENT

This amendment addresses safety update based on recent post marketing safety monitoring findings. Sponsor has conducted a comprehensive review of safety data from post-marketing use with alemtuzumab, updated contraindications for retreatment with alemtuzumab, and updated Adverse Event of Special Interest (AESI) list and identified areas where risk mitigation measures will be implemented that include increasing frequency of liver function tests from every 3 months to every month.

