### **6.2.2 Determination of end of clinical trial (all patients)**

The end of the clinical trial occurs 5 years (plus a window of 6 months) after the inclusion of the first patient.

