### 3. Amended Clinical Trial Protocol 02 (24-Jul-2019)

This amended protocol is considered to be substantial based on the criteria set forth in Article 10(a) of Directive 2001/20/EC of the European Parliament and the Council of the European Union because it significantly impacts the safety or physical/mental integrity of participants.

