**Protocol amendment summary of changes table**

| Section # and Name                             | Description of Change  | Brief Rationale   |
|--|--|---|
| 1.2.2 Re-treatment with alemtuzumab chart flow | Add liver function test along with TSH footnote b:
... LFT includes: ALT, AST, ALP, albumin, total protein and bilirubin.   | Monitoring potential autoimmune hepatitis                 |
| 4 INTRODUCTION AND RATIONALE                   | Add the following text:
...
During post-marketing use, additional risks of alemtuzumab have been identified recently that include: 
 
• Stroke (hemorrhagic and ischemic).
 
• Cervicocephalic (ie, vertebral, carotid) arterial dissection.
 
• Pulmonary alveolar hemorrhage.
 
• Acute acalculous cholecystitis.
 
• Autoimmune hepatitis.
 
• Hemophagocytic lymphohistiocytosis (HLH).
 
 Cases of serious and life-threatening stroke (including hemorrhagic and ischemic), myocardial infarction and cervicocephalic (ie, vertebral, carotid) arterial dissection have been reported | Update recent safety findings and benefit risk assessment |

| Section # and Name  | Description of Change   | Brief Rationale                           |
|---|---|---|
|   | 
within three days of alemtuzumab administration, with most cases occurring within one day. Cases of pulmonary alveolar hemorrhage have been reported with onset within 48 hours of alemtuzumab infusion. Long term auto immune risks, such as cases of Hemophagocytic lymphohistiocytosis (HLH) and autoimmune hepatitis causing clinically significant liver injury, including acute liver failure requiring transplant, has been reported. To minimize the risk of these serious adverse events, recommendations are provided for infusion related management and long term safety monitoring for patients receiving re-treatment of alemtuzumab during the course of the trial
 
 
• Pre infusion: assess overall health status and risk factors; baseline BP/HR, bleeding risk, platelets count. Baseline liver function test.
 
• During infusion: continuous or hourly monitoring BP/HR; intermittently ambulation, compressive stocking.
 
• Post infusion: inform/remind patient any abnormal clinical sign/symptoms related to infusion.
 
• Periodic liver function test.
 
 |   |

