#### **2.4.5.3 Analyses of laboratory variables**

Laboratory analysis will be conducted for retreated population and 48 months follow-up population. The baselines for each population are defined as below.

- Retreated population baseline: The last non-missing assessment prior to first dose of alemtuzumab in TOPAZ study. The baseline should be taken within 2 weeks prior to the treatment for laboratory assessment except for HPV and pregnancy test. For HPV and pregnancy test, it can be taken in 12 months before the treatment.
- 48 months follow-up population baseline: The last non-missing assessment prior to the last dose of alemtuzumab in previous studies. The baseline should be taken within 2 weeks

prior to the treatment for laboratory assessment except for HPV and pregnancy test. For HPV and pregnancy test, it can be taken in 12 months before the treatment.

The summary statistics (including number, mean, median, Q1, Q3, standard deviation, minimum and maximum) of all laboratory variables (central laboratory values and changes from baseline) will be calculated for each visit or study assessment (baseline, each postbaseline time point, last on-treatment and/or worst on-treatment value and/or other specific assessment) in overall group and by subgroups (IAT vs DAT). This section will be organized by biological function [Section 2.1.4.3](#).

The incidence of PCSAs (list provided in [Appendix A](#)) at any time during the treatment-emergent adverse event period will be summarized by biological function and in overall group and by subgroups (IAT vs DAT) whatever the baseline level and/or according to the following baseline status categories:

- Normal/missing
- Abnormal according to PCSA criterion or criteria

For parameters for which no PCSA criteria are defined, similar table(s) using the normal range will be provided.

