#### ***Drug-induced liver injury***

The liver function tests, namely AST, ALT, alkaline phosphatase, direct bilirubin and total bilirubin, are used to assess possible drug-induced liver toxicity. The proportion of patients with PCSA values at any postbaseline visit by baseline status will be displayed in overall group and by subgroups (IAT vs DAT) for each parameter.

Time to onset of the initial ALT and AST elevation ( $>3$  x ULN) and total bilirubin elevation ( $>2$  x ULN) (time to first observation of ALT  $> 3$  x ULN or total bilirubin  $> 2$  x ULN, whichever comes first) will be analyzed using Kaplan-Meier estimates, using the midpoint of the time interval between the first assessment showing the elevation and the previous assessment, presented in overall group and by subgroups (IAT vs DAT).

Listing of possible Hy's law cases identified (eg, patients with any elevated ALT $>3$  x ULN, and associated with an increase in bilirubin  $\geq 2$  x ULN) with ALT, AST, alkaline phosphatase and total bilirubin.

Summarize the incidence of liver-related adverse events in overall group and by subgroups (IAT vs DAT). The selection of preferred terms will be based on the hepatic disorder SMQ.

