***Handling of potentially clinically significant abnormalities***

If a patient has a missing baseline he will be grouped in the category “normal/missing at baseline.”

For PCSAs with 2 conditions, one based on a change from baseline value or a normal range and the other on a threshold value, with the first condition being missing, the PCSA will be based only on the second condition.

For a PCSA defined on a threshold and/or a normal range, this PCSA will be derived using this threshold if the normal range is missing; eg, for eosinophils the PCSA is  $> 0.5$  GIGA/L or  $>ULN$  if  $ULN \geq 0.5$  GIGA/L. When ULN is missing, the value 0.5 should be used.

Measurements flagged as invalid by the laboratory will not be summarized or taken into account in the computation of PCSA values.

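### The SAP's liver-injury analysis assumes monthly liver tests, but these were scheduled only from July 2019 (every 3 months) and January 2020 (monthly), so onset times and results by baseline status are unreliable for patients dosed earlier

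*SAP*

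**What the plan says.** **When liver tests were scheduled.** Protocol Appendix E lists liver tests as additions made by Amended Protocol 02 of 24-Jul-2019. The flow-chart entry begins "Add liver function test along with TSH", and the entry for Section 9.5.2.2 sets a test before retreatment and then one every 3 months for 48 months. The rationale for Amended Protocol 03 (28-Jan-2020) describes "increasing frequency of liver function tests from every 3 months to every month". The original protocol dates from 11-Apr-2014. On study length, Protocol 6.2.2 says: "The end of the clinical trial occurs 5 years (plus a window of 6 months) after the inclusion of the first patient".

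**What the SAP assumes.** SAP 2.1.4.3 describes monthly liver function sampling both for patients dosed within 48 months before entry and for patients retreated in the study. SAP 2.5.3.1 builds monthly analysis windows for retreated patients. Neither mentions that the schedule began late.

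**How liver injury is analysed.** Laboratory analyses cover the retreated and the 48-month follow-up populations (SAP 2.4.5.3). The Kaplan-Meier onset date is set "using the midpoint of the time interval between the first assessment showing the elevation and the previous assessment". On baseline, the section says: "The baseline should be taken within 2 weeks prior to the treatment for laboratory assessment except for HPV and pregnancy test". SAP 2.5.2 says "If a patient has a missing baseline he will be grouped in the category" that combines normal with missing.

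**The concern.** A midpoint rule is harmless when tests are a month apart. It is not harmless when the interval spans a period in which the protocol asked for no liver test. The Kaplan-Meier also has no stated time origin, entry rule or censoring rule, and no rule for a patient whose first liver test is already elevated.

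The baseline rule adds to this. A patient infused before July 2019 had no protocol-scheduled liver test beforehand. If no value exists, the patient joins the normal group, and a new elevation cannot be told from an unknown starting point.

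Safety is the primary objective, autoimmune hepatitis is a listed event of special interest, and it is a stated reason for both amendments. The laboratory liver outputs will be read as evidence on that risk.

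The amendment log is used here only to date when scheduled measurements could begin. The point is not that old and current text differ.

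**Working it through.** The documents give no incidence, event count or precision target for liver injury, so there is no planned figure to reproduce. Two checks are possible.

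**1. Calendar coverage of scheduled liver tests.**

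Inputs: study window 60 + 6 = 66 months from first inclusion (Protocol 6.2); tests scheduled from 24-Jul-2019; monthly from 28-Jan-2020. The first-inclusion date is not given, so a range is assumed:
- 28-Jul-2014: 66 months before Amended Protocol 03, so the study would only just still be open.
- 23-Mar-2016: date of the US amendment, as an intermediate case.
- 27-Feb-2018: the amendment of that date already refers to ongoing patients.

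Months = days / 30.4375. The 3-monthly phase is 188 / 30.4375 = 6.2 months.

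| Assumed first inclusion | Before any scheduled liver test | Share of 66 months | Remaining months | Of which monthly |
|---|---|---|---|---|
| 28-Jul-2014 | 1822 days = 59.9 | 91% | 66 − 59.9 = 6.1 | about 0 |
| 23-Mar-2016 | 1218 days = 40.0 | 61% | 66 − 40.0 = 26.0 | 26.0 − 6.2 = 19.8 |
| 27-Feb-2018 | 512 days = 16.8 | 25% | 66 − 16.8 = 49.2 | 49.2 − 6.2 = 43.0 |

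These are shares of the study calendar, not of post-infusion person-time. The latter needs infusion dates, which the documents do not give.

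**2. Dating error of the midpoint rule.**

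Let g be the gap between the last non-elevated and the first elevated test. True onset lies somewhere in the gap. The maximum error of the midpoint is g/2. If onset is uniform over the gap, the mean absolute error is g/4.

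| Gap (months) | Maximum error | Mean absolute error |
|---|---|---|
| 1 | 0.5 | 0.25 |
| 3 | 1.5 | 0.75 |
| 12 | 6 | 3 |
| 24 | 12 | 6 |
| 48 | 24 | 12 |

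Long gaps can follow from the SAP's own rules. For the 48-month follow-up population, baseline is the last value before the last dose in an earlier study. Apart from baseline, SAP 2.4.5 uses only data collected in TOPAZ. The previous assessment for a first elevated TOPAZ test can therefore be a pre-dose value from well before entry. If there is no earlier value, the midpoint cannot be computed.

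**3. Passages that disagree on who is tested.** For patients dosed within 48 months before entry, Protocol 9.5.2.1 lists blood count, creatinine, urinalysis, TSH and HPV screening, but no liver test. Protocol 10.1.1 sends the same patients to Section 10.1.6.2, which does list liver tests. SAP 2.1.4.3 lists them too.

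**The case against.** A reader might infer that the SAP counts all earlier time as monitored and so understates liver toxicity. The documents do not support that.

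- **Risk set.** The SAP never says that untested time counts as event-free; it is silent. If such time were counted, early Kaplan-Meier incidence would be too low, but this remains conditional.
- **Direction.** SAP 2.4.5 bases the denominator for clinically significant abnormalities on patients assessed for the parameter. If early tests were done for clinical reasons, that percentage could be too high. The midpoint can fall before or after true onset.
- **Unscheduled data.** The amendment dates fix when tests were scheduled, not when values can exist. Protocol 10.1.5 records all procedures done at unscheduled visits, and SAP 2.5.4 uses unscheduled laboratory values. Protocol 8.1.2 refers pre-treatment checks to the investigator's brochure or local label, which are not available here. It therefore cannot be said that most early baselines are missing.
- **Other outputs.** Hepatic-SMQ adverse events, the special-interest event tables and expedited ALT reporting do not use the midpoint or the Kaplan-Meier risk set. Abnormalities may also be shown regardless of baseline level. The safety analysis is descriptive.

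All of this stands, and it limits the point. It does not supply a gap limit, an entry rule, a censoring rule or a rule for a missing previous test. Nor does it separate missing from normal baselines, and silent elevations still need a test to be found.

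**Conclusion.** The point holds as a moderate, inexpensive correction. For patients dosed before liver testing was scheduled, the SAP's rules give unreliable onset times and unreliable incidence by baseline status.

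The dating error is at most 0.5 month with monthly and 1.5 months with 3-monthly tests, but reaches 24 months if a 48-month gap is bridged. Between 25% and 91% of the study calendar precedes any scheduled liver test, under the assumed first-inclusion dates. Because ethics approval precedes implementation (Protocol 15), site start dates may be later than the amendment dates.

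The net bias cannot be sized: first-inclusion dates, retreatment dates and the extent of unscheduled testing are not given. Its direction may differ between the Kaplan-Meier and the abnormality percentages. A general statement that liver toxicity is understated would go beyond the documents.

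**What to change.** Amend SAP 2.4.5.3 as follows.

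(a) Treat onset as interval-censored between the last non-elevated and the first elevated liver test. Keep the midpoint only where that gap is within one scheduled interval. State the time origin, start risk time at the first available post-infusion liver test, and censor at the last liver test. Report patients already elevated at their first test separately as prevalent.

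(b) For liver parameters, show missing baseline apart from normal.

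(c) Report the number of patients and person-months with liver testing, and present results separately for infusions before and after 24-Jul-2019.

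(d) Limit laboratory-based liver conclusions to tested time, with the hepatic-SMQ adverse events alongside.

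Two simpler repairs would not serve. Using the detection date across long gaps has maximum error g and mean error g/2, twice the midpoint's, and never dates onset early. Starting risk time at the first scheduled test gives patients already elevated then no time at risk, and discards earlier unscheduled results.

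Protocol 9.5.2.1 must be reconciled with Protocol 10.1.6.2 and SAP 2.1.4.3 on liver testing for patients dosed within 48 months before entry.

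The analysis changes need only SAP wording and some extra programming, with no new data collection. The price is fewer patients at risk and wider intervals.

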#### **2.4.5.4 Analyses of vital sign variables**

Vital sign analysis will be done for all safety population and for retreated population.

The infusion related vital sign analysis will be done separately for retreated population. The baseline for infusion related analysis is the assessment taken before steroid administration.

The summary statistics (including number, mean, median, Q1, Q3, standard deviation, minimum and maximum) of all vital signs variables (central laboratory values and changes from baseline) will be calculated for each visit or study assessment (baseline, each postbaseline time point, last on-treatment and/or worst on-treatment value and/or other specific assessment) in overall group and by subgroups (IAT vs DAT). For parameters provide a list of parameters for which plots will be displayed; mean changes from baseline with the corresponding standard error will be plotted over time (at same time points) in overall group and by subgroups (IAT vs DAT).

The incidence of PCSAs at any time during the treatment-emergent adverse event period will be summarized in overall group and by subgroups (IAT vs DAT) irrespective of the baseline level and/or according to the following baseline status categories:

- Normal/missing
- Abnormal according to PCSA criterion or criteria

#### **2.4.5.5 Analyses of electrocardiogram variables**

By-patient listing will be provided for retreated patients as needed.

#### **2.4.6 Analyses of quality of life/health economics variables**

Descriptive statistics for observe value, change from baseline as well as percentage change from baseline will be presented in reference of long-term baseline from prior studies by subgroups (IAT vs DAT). MMRM model may be applied if necessary as supportive.

### **2.5 DATA HANDLING CONVENTIONS**

#### **2.5.1 General convention**

For long-term analysis, the reference date is the date of first alemtuzumab or SC IFNB-1a treatment in prior studies.

#### **2.5.2 Missing data**

For categorical variables, patients with missing data are not included in calculations of percentages unless otherwise specified. When relevant, the number of patients with missing data is presented.

#### ***Handling of computation of treatment duration if investigational medicinal product end of treatment date is missing***

For the calculation of the treatment duration, the date of the last dose of IMP is equal to the date of last administration reported on the end-of-treatment case report form page. If this date is missing, the exposure duration should be left as missing.

The last dose intake should be clearly identified in the case report form and should not be approximated by the last returned package date.

***Handling of medication missing/partial dates***

No imputation of medication start/end dates or times will be performed. If a medication date or time is missing or partially missing and it cannot be determined whether it was taken prior or concomitantly, it will be considered a concomitant medication.

***Handling of adverse events with missing or partial date/time of onset***

Missing or partial adverse event onset dates and times will be imputed so that if the partial adverse event onset date/time information does not indicate that the adverse event started prior to treatment or after the treatment-emergent adverse event period, the adverse event will be classified as treatment-emergent. No imputation of adverse event end dates/times will be performed. These data imputations are for categorization purpose only and will not be used in listings. No imputation is planned for date/time of adverse event resolution.

***Handling of adverse events when date and time of first investigational medicinal product administration is missing***

When the date and time of the first IMP administration is missing, all adverse events that occurred on or after the day of randomization should be considered as treatment-emergent adverse events. The exposure duration should be kept as missing.

The last dose intake should be clearly identified in the case report form and should not be approximated by the last returned package date.

***Handling of missing assessment of relationship of adverse events to investigational medicinal product***

If the assessment of the relationship to IMP is missing, then the relationship to IMP has to be assumed and the adverse event considered as such in the frequency tables of possibly related adverse events, but no imputation should be done at the data level.

***Handling of missing severity/grades of adverse events***

If the severity/grade is missing for 1 of the treatment-emergent occurrences of an adverse event, the maximal severity on the remaining occurrences will be considered. If the severity is missing for all the occurrences, a “missing” category will be added in the summary table.

***Handling of potentially clinically significant abnormalities***

If a patient has a missing baseline he will be grouped in the category “normal/missing at baseline.”

For PCSAs with 2 conditions, one based on a change from baseline value or a normal range and the other on a threshold value, with the first condition being missing, the PCSA will be based only on the second condition.

For a PCSA defined on a threshold and/or a normal range, this PCSA will be derived using this threshold if the normal range is missing; eg, for eosinophils the PCSA is  $> 0.5$  GIGA/L or  $>ULN$  if  $ULN \geq 0.5$  GIGA/L. When ULN is missing, the value 0.5 should be used.

Measurements flagged as invalid by the laboratory will not be summarized or taken into account in the computation of PCSA values.

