### 1.3 DETERMINATION OF SAMPLE SIZE

There are no sample size calculations for this long-term safety study. Sample size will be based on elective participation of patients who were enrolled (and completed at least 48 months) into the CAMMS03409 extension study.

[figure not shown]

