#### **General common rules**

All safety analyses will be performed on the safety population as defined in [Section 2.3.1.1](#), unless otherwise specified, using the following common rules:

- The baseline value is defined as the available value assessed on or prior to the V01 Selection visit, unless otherwise specified. If laboratory, vital sign and physical examinations were performed in CAMMS03409 study within the pre-specified time-windows, then the last assessment within the time-window can be considered as baseline when the corresponding V01 assessments are missing.
- The potentially clinically significant abnormality (PCSA) values are defined as abnormal values considered medically important by the Sponsor according to predefined criteria/thresholds based on literature review and defined by the Sponsor for clinical laboratory tests and vital signs (PCSA version dated May 2014 [[Appendix A](#)])
- PCSA criteria will determine which patients had at least 1 PCSA during the treatment-emergent adverse event period, taking into account all evaluations performed during the treatment-emergent adverse event period, including nonscheduled or repeated evaluations.

The number of all such patients will be the numerator for the on-treatment PCSA percentage

- The treatment-emergent PCSA denominator by group for a given parameter will be based on the number of patients assessed for that given parameter in the treatment-emergent adverse event period in overall group and by subgroups (IAT vs DAT) on the safety population.
- For quantitative safety parameters based on central laboratory/reading measurements, descriptive statistics will be used to summarize results and change from baseline values by visit and analysis group.
- The analysis of the safety variables will be essentially descriptive and no systematic testing is planned.

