eGFR (mL/min/1.73m2) (Estimate of GFR based on an MDRD equation)	<15 (end stage renal disease) ≥15 - <30 (severe decrease in GFR) ≥30 - < 60 (moderate decrease in GFR) ≥60 - <90 (mild decrease in GFR) ≥90 (normal GFR)	FDA draft Guidance 2010 Pharmacokinetics in patients with impaired renal function-study design, data analysis, and impact on dosing and labeling
Creatinine	≥150 µmol/L (Adults) ≥30% change from baseline ≥100% change from baseline	Benichou C., 1994.
Uric Acid Hyperuricemia Hypouricemia	>408 µmol/L <120 µmol/L	Harrison- Principles of internal Medicine 17 th Ed., 2008.
Blood Urea Nitrogen	≥17 mmol/L	
Chloride	<80 mmol/L >115 mmol/L	
Sodium	≤129 mmol/L ≥160 mmol/L	
Potassium	<3 mmol/L ≥5.5 mmol/L	FDA Feb 2005.
Total Cholesterol	≥7.74 mmol/L	Threshold for therapeutic intervention.
Triglycerides	≥4.6 mmol/L	Threshold for therapeutic intervention.
Lipasemia	≥3 ULN	

**CRITERIA for POTENTIALLY CLINICALLY SIGNIFICANT ABNORMALITIES  
for Phase 2/3 studies (oncology excepted)  
(Version 3.0 May 2014)**

Parameter	PCSA	Comments
Amylasemia	≥3 ULN	
Glucose		
Hypoglycaemia	≤3.9 mmol/L and <LLN	ADA May 2005.
Hyperglycaemia	≥11.1 mmol/L (unfasted); ≥7 mmol/L (fasted)	ADA Jan 2008.
HbA1c	>8%	
Albumin	≤25 g/L	
CRP	>2 ULN or >10 mg/L (if ULN not provided)	FDA Sept 2005.
Hematology		
WBC	<3.0 GIGA/L (Non-Black); <2.0 GIGA/L (Black) ≥16.0 GIGA/L	Increase in WBC: not relevant. To be interpreted only if no differential count available.
Lymphocytes	>4.0 GIGA/L	
Neutrophils	<1.5 GIGA/L (Non-Black); <1.0 GIGA/L (Black)	International Consensus meeting on drug-induced blood cytopenias, 1991. FDA criteria.
Monocytes	>0.7 GIGA/L	
Basophils	>0.1 GIGA/L	
Eosinophils	>0.5 GIGA/L or >ULN (if ULN ≥0.5 GIGA/L)	Harrison- Principles of internal Medicine 17 th Ed., 2008.
Hemoglobin	≤115 g/L (Male); ≤95 g/L (Female) ≥185 g/L (Male); ≥165 g/L (Female)  Decrease from Baseline ≥20 g/L	Criteria based upon decrease from baseline are more relevant than based on absolute value. Other categories for decrease from baseline can be used (≥30 g/L, ≥40 g/L, ≥50 g/L).
Hematocrit	≤0.37 v/v (Male) ; ≤0.32 v/v (Female) ≥0.55 v/v (Male) ; ≥0.5 v/v (Female)	
RBC	≥6 Tera/L	Unless specifically required for particular drug development, the analysis is redundant with that of Hb. Otherwise, consider FDA criteria.
Platelets	<100 GIGA/L ≥700 GIGA/L	International Consensus meeting on drug-induced blood cytopenias, 1991.

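### Criteria defined only by change from baseline are diluted by patients who have no baseline, and the combined normal/missing row hides who those patients are

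*SAP*

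**What the plan says.** **Denominator.** Under General common rules in SAP 2.4.5, the PCSA denominator for a parameter "will be based on the number of patients assessed for that given parameter in the treatment-emergent adverse event period". Nothing there requires a baseline value.

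**Criteria.** SAP Appendix A lists some criteria that consist only of a change from baseline: creatinine (≥30% and ≥100%), hemoglobin ("Decrease from Baseline ≥20 g/L") and weight (5% up or down). Creatinine and hemoglobin also have absolute thresholds, listed as separate criteria.

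**Missing baseline.** Under the PCSA heading of SAP 2.5.2: "If a patient has a missing baseline he will be grouped in the category" normal/missing at baseline. SAP 2.4.5.3 (laboratory) and 2.4.5.4 (vital signs) plan the PCSA summary with two status rows, normal/missing and abnormal. The laboratory summary is to be shown "whatever the baseline level and/or according to the following baseline status categories".

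**Fallback.** SAP 2.5.2 also covers PCSAs that combine a change or normal-range condition with a threshold: "with the first condition being missing, the PCSA will be based only on the second condition". In Appendix A the change-plus-threshold form applies to heart rate and systolic and diastolic blood pressure. No rule is given for a criterion whose only condition is a change.

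**Baseline window.** For both laboratory populations, SAP 2.4.5.3 states: "The baseline should be taken within 2 weeks prior to the treatment for laboratory assessment except for HPV and pregnancy test". For the 48 months follow-up population, that baseline lies before the last dose in an earlier study.

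**The concern.** Changes in laboratory parameters are among the primary endpoints (Protocol 9.1). Creatinine change bears on nephropathy and hemoglobin fall on cytopenia, and both conditions are adverse events of special interest. The Appendix A comments rate the hemoglobin change criteria as more relevant than the absolute ones.

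Two separate faults follow from the rules above.

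- **Dilution.** A patient with no baseline cannot be an event on a change-only criterion but is still assessed for the parameter. Counted in the denominator, that patient is treated as event-free.
- **Mixed row.** Patients with a normal baseline and patients with an unknown one share a row. To recover the rate among truly normal patients, a reader needs both the number with a missing baseline and the abnormalities among them. The planned rows show neither.

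**Working it through.** The documents give no figure to reproduce. On sample size the SAP says "There are no sample size calculations for this long-term safety study", and it states no missing-baseline rate. Every rate below is therefore an assumption, shown over a range.

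**Step 1. Which rule sets the denominator?** The general missing-data rule in SAP 2.5.2 leaves patients with missing data out of percentages for categorical variables, unless something else is specified. SAP 2.4.5 does specify something else for PCSAs: patients assessed for the parameter. As the specific rule it governs, and it includes patients without a baseline.

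**Step 2. Change-only criteria.** Let p be the true rate and m the share of assessed patients without a baseline, with p the same whether or not a baseline exists. Then:

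reported rate = p × (1 − m)

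With p assumed at 8%:

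| m | Calculation | Reported |
|---|---|---|
| 5% | 8% × 0.95 | 7.6% |
| 10% | 8% × 0.90 | 7.2% |
| 20% | 8% × 0.80 | 6.4% |
| 30% | 8% × 0.70 | 5.6% |

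Under the general rule in 2.5.2 the figure would stay at 8%.

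**Step 3. The normal/missing row for threshold criteria.** Let q be the share truly abnormal at baseline, pN and pA the later PCSA rates in truly normal and truly abnormal patients, and k the relative detection of abnormalities in patients without a baseline. Then:

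- pM = k × [(1 − q) × pN + q × pA], the rate in patients without a baseline
- w = m / [m + (1 − m)(1 − q)], their share of the row
- row rate = (1 − w) × pN + w × pM

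*Equal detection (k = 1), with q = 10%, pN = 3%, pA = 80%.* The row rate simplifies to [0.9 × 0.03 + m × 0.1 × 0.8] / [(1 − m) × 0.9 + m]:

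- m = 5%: 0.031 / 0.905 = 3.43%
- m = 20%: 0.043 / 0.92 = 4.67%
- m = 30%: 0.051 / 0.93 = 5.48%

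The true rate in normal patients is 3.0% in each case.

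*Can the direction reverse?* Take m = 10%, q = 5%, pN = 5%, pA = 50%:

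- w = 0.10 / (0.10 + 0.90 × 0.95) = 0.105
- pM at k = 1 is 0.95 × 5% + 0.05 × 50% = 7.25%, and the row shows 5.24%
- Break-even is k = 5 / 7.25 = 0.69
- At k = 0.5 the row shows 4.86%, below the true 5.00%

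The row is inflated only if patients without a baseline have more detected abnormalities than truly normal ones.

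**The case against.** **Compliant re-treated patients will have a baseline.** Protocol 9.5.2.2 and 10.1.6.1 require blood count and creatinine before re-treatment unless done within 2 weeks, which matches the SAP window. This stands for creatinine and hemoglobin and keeps m low in that group. It says nothing about the 48 months follow-up population, whose earlier-study sampling cannot be checked here. A baseline in an earlier study is not for that reason missing.

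**The general missing-data rule could remove the dilution.** A programmer might apply it. The specific PCSA rule points the other way, so at best the SAP supports two readings with different percentages. That is itself a reason to settle it.

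**Late introduction of liver tests.** According to Protocol Appendix E, liver tests before re-treatment came in with Amended Protocol 02 in July 2019. A reader might infer that this feeds the dilution. It does not: the Appendix A liver criteria contain no change from baseline. It bears only on the normal/missing row, which SAP 2.4.5.3 also uses for liver PCSAs.

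**Other safeguards.** Nephropathies and cytopenias are captured as adverse events of special interest, absolute thresholds need no baseline, and "The analysis of the safety variables will be essentially descriptive and no systematic testing is planned". This stands and limits the consequence. It does not correct the change-only percentages.

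**The two-condition fallback.** It can count a long-standing value beyond the threshold as an event. It is nonetheless explicit, prespecified and leans toward detection, so replacing it is a matter of choice.

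**Conclusion.** The point holds, with limited scope. Applied as written, the SAP multiplies the incidence of change-only PCSAs by (1 − m). That is a relative loss of 5% to 30% over the assumed range of m, for example 7.6% to 5.6% in place of 8%. The factor assumes that the PCSA denominator rule overrides the general missing-data rule and that patients without a baseline share the same true rate. The actual m is not in the documents and may be small.

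The normal/missing row conceals the rate among truly normal patients and may distort it. A reader might go further in three ways that the documents do not support:

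- **That missing baselines are reported as normal.** The row is openly labelled normal/missing.
- **That new abnormalities are necessarily overstated.** The direction depends on who lacks a baseline and can reverse, as shown.
- **That one table overstates while another understates.** Both effects arise in the same PCSA summary; the first concerns threshold criteria and the second change-only criteria.

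**What to change.** In SAP 2.4.5 and 2.5.2:

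1. For criteria defined only by change from baseline (creatinine ≥30% and ≥100%, hemoglobin fall, weight), use as denominator the patients with a baseline and at least one post-baseline value, and print that number.
2. Replace the two baseline-status rows with three: normal, abnormal and missing. SAP 2.5.2 already adds a missing category for adverse events whose severity is missing at every occurrence, so the device is not new to this plan.
3. Keep the threshold-only fallback for heart rate and blood pressure. The missing-baseline row then shows how many events rest on it.

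The cost is SAP wording and table shells, with no new data. The downside is one extra row per parameter and slightly smaller denominators for the change-only criteria.
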